6.10.2. Sensitivity Analyses

Sensitivity analyses are included to demonstrate robustness of analyses methods using different missing data imputations, populations, and analyses assumptions. Supplementary analysis for the primary endpoints and sensitivity analyses for secondary endpoints are described in [Table KGAK.6.6](#) and [Table KGAK.6.7](#).

6.10.3. Secondary Efficacy Analyses

Secondary outcomes and the analyses are described in [Table KGAK.6.6](#) and [Table KGAK.6.7](#).

6.11. Health Outcomes/Quality-of-Life Analyses

Analyses of Pruritus NRS, Sleep-loss NRS, Skin pain NRS, POEM, and PROMIS are described in [Table KGAK.6.6](#) and [Table KGAK.6.7](#).

6.12. Bioanalytical and Pharmacokinetic/Pharmacodynamic Methods

Details of pharmacokinetic (PK)/pharmacodynamic (PD) analyses can be found in a separate PK/PD analysis plan.

6.13. Safety Analyses

The planned analyses of safety data will be performed with an intent to maintain consistency with compound level standard safety analyses. These standards are based on internal standards that were informed by Clinical Data Interchange Standards Consortium (CDISC) standards, regulatory guidance (for example, FDA Clinical Review Template), and cross-industry standardization efforts (for example, Pharmaceutical Users Software Exchange [PhUSE] white

papers from the Standard Analyses and Code Sharing Working Group provided in the PhUSE Computational Science Deliverables Catalog).

Safety evaluations will be based upon the Modified Safety Population (Treatment Period) and Safety Population (Treatment Period).

Analysis populations are fully defined in [Table KGAK.6.1](#) while [Table KGAK.6.2](#) describes the treatment groups, associated study periods, and the comparisons for each analysis population.

For document writing purposes for safety, tests with 2-sided p-values less than .05 will be referred to as having strong statistical evidence for a treatment difference, unless otherwise noted. However, p-values should not be over-interpreted for these safety analyses. Except for prespecified hypotheses, they correspond to data-driven hypotheses and hence are only useful as a flagging mechanism.

Not all displays described in this section will necessarily be included in the CSRs. Any display described and not provided in the CSR will be available upon request. Not all displays will necessarily be created as a “static” display. Some may be incorporated into interactive display tools instead of or in addition to a static display. Any display created interactively will be included in the CSR if deemed relevant to the discussion.

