For variables that are not collected at each postbaseline visit, data may exist at visits where the variable was not scheduled to be collected. In these situations, data from the early discontinuation visit that do not correspond to the planned collection schedule will be excluded from the MMRM analysis (Andersen and Millen 2013). Also, for by-visit summaries/displays such as boxplots, the weeks when data were not scheduled to be collected may not be displayed. However, unscheduled assessments within any defined study period will still be used in the shift analyses and for imputing values for the change from baseline to last observation carried forward (LOCF) endpoint analyses.

Unless specified otherwise, Fisher's exact test will be used for adverse events (AEs) and other categorical safety measures. Odds ratios will be created with lebrikizumab treatment as the numerator and placebo as the denominator. Continuous vital sign and laboratory values will be analyzed by an ANCOVA with treatment and baseline value in the model.

There will be no adjustment for multiple comparisons.

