Statistical comparisons will be performed using Fisher's exact test. Odds ratio will be provided. For AE related listings, AEs occurring on or after the date of Informed Consent and before the date of first injection in KGAK study will also be reported if proper.

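### SAP 6.13 labels every unadjusted safety p<.05 as strong evidence of a treatment difference, although the same paragraph calls such p-values only a flag; with no drug effect, the laboratory panel alone would probably trigger the label at least once

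*SAP*

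**What the plan says.** SAP 6.13 opens its rule by limiting it to document-writing purposes, then states that "tests with 2-sided p-values less than .05 will be referred to as having strong statistical evidence for a treatment difference", unless otherwise noted. I found no exception in the safety sections; the nearest is SAP 6.13.1, where exposure summaries carry no p-values at all.

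The two sentences that follow pull the other way: "However, p-values should not be over-interpreted for these safety analyses", and "Except for prespecified hypotheses, they correspond to data-driven hypotheses and hence are only useful as a flagging mechanism".

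Three other places fix the scope:

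- SAP 6.1.2: "There will be no adjustment for multiple comparisons".
- SAP 6.1.2: "Continuous vital sign and laboratory values will be analyzed by an ANCOVA with treatment and baseline value in the model". Table KGAK.6.9 repeats this ANCOVA for the laboratory change from baseline to last observation. Table KGAK.6.10, for vital signs, lists only box plots, scatterplots and treatment-emergent high/low tables.
- SAP 6.1.2 and 6.13.2: adverse events are compared by Fisher's exact test, and "Odds ratio will be provided". Neither section names a confidence interval for adverse events.

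Protocol 9.1 calls the study descriptive, with no planned hypothesis testing. The carve-out for prespecified hypotheses therefore covers no safety comparison.

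**The concern.** A result cannot be both strong statistical evidence and only a flag. The caution tells the writer how to think about a p-value, while the label sets the words used for it. A reader of the report meets the label.

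With no adjustment and a long fixed list of tests, p<.05 somewhere is the expected outcome even for a drug with no effect on any analyte. A report that follows the convention could then describe a chance laboratory shift as strongly evidenced.

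A smaller, related gap concerns adverse events that are not labelled. A p-value and an odds ratio without an interval do not show how large an excess the data still allow.

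**Working it through.** **The plan's own figures.** The SAP states no false-flag rate for safety. Its only design figures are the 90% Wald half-widths in SAP 5.2, from 1.645 × √(2p(1−p)/109). At p = 0.83 this gives 0.0837, and at p = 0.90 it gives 0.0668. These match the stated 0.08 and 0.07 but do not bear on safety labelling.

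**Inputs.**
- Test level: 0.05 two-sided, unadjusted (SAP 6.1, 6.1.2, 6.13).
- Laboratory tests: Protocol Appendix 10.2 lists 13 numeric hematology and 21 numeric chemistry analytes, 13 + 21 = 34. Cell morphology and urinalysis are left out.
- Vital signs: temperature, respiratory rate, pulse, systolic and diastolic pressure = 5 (Protocol 8.2.2).
- Arm size: about 240 randomized 1:1, so about 120 per arm before the two excluded sites are removed.
- Correlation between tests and adverse event rates: not in the documents. Both are assumed, and ranges are shown.

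**Chance of at least one label with no drug effect, independent tests.** The formula is 1 − 0.95^m.
- m = 14: 51.2%, the first m above one half.
- m = 34 (laboratory only): 82.5%, with 34 × 0.05 = 1.7 false labels expected.
- m = 39 (if the five vital signs are tested by ANCOVA as SAP 6.1.2 says): 86.5%, with 39 × 0.05 = 1.95 expected.

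**Correlated tests, 34 laboratory analytes.** Correlated normal test statistics were simulated 100,000 times, counting runs with any |z| > 1.96.

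| Assumed structure | P(at least one label) |
|---|---|
| Related analytes clustered, within-cluster correlation 0.5 | 80% |
| Same, 0.8 | 76% |
| Same, 0.95 | 71% |
| One common correlation, 0.3 | 70% |
| One common correlation, 0.5 | 54% |
| One common correlation, 0.6 | 45% |

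The clusters were hemoglobin/hematocrit/red cells, the three red-cell indices, white cells/neutrophils, the three bilirubins, ALT/AST/GGT, urea nitrogen/creatinine, sodium/chloride, and total protein/albumin/calcium. The other 13 analytes were independent.

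**Adverse event tables alone.** Fisher's test is conservative for uncommon events. At 120 per arm its true size is about 0.1% at a 1% event rate, 0.7% at 2% and 2.1% at 5%. With no events in the other arm, 6 are needed: 6 vs 0 gives p = 0.029, 5 vs 0 gives p = 0.060. Two assumed profiles, of 49 and 75 preferred terms, give a 23% and a 41% chance of at least one label. The high frequency therefore comes from the laboratory ANCOVA panel, not from the adverse event tables.

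**What an unlabelled adverse event leaves open.** Exact Fisher power at 120 per arm, rates assumed, is 39% for 3% vs 9% and 22% for 2% vs 6%. For illustration, 9 vs 3 events gives p = 0.14 and no label. The risk difference is 9/120 − 3/120 = 5.0 percentage points, with a Newcombe 95% interval from −0.8 to 11.4 points.

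**The case against.** The best defence is that SAP 6.13 corrects itself within the paragraph. The rule is a writing convention, the caution follows at once, and the absence of adjustment is disclosed. That stands in part: multiplicity is not hidden, and what remains is a clash of wording. But the caution does not withdraw the label.

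Three stronger readings are tempting, and the documents do not support them.

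- *A null trial's report would usually announce strong evidence.* SAP 6.13 fixes how a p<.05 is referred to. It does not require each one to be discussed, and it says not every display will be in the report. The frequency also rests on assumed correlation: at a common 0.6 it falls below one half. That would need analytes as different as sodium, platelets and ALT all to be correlated at about that level. Clustering is more plausible, but it is still an assumption.
- *A tripling of an adverse event of special interest would usually go unlabelled.* The documents give no event rates, and this fails in general. At 120 per arm, Fisher's test flags 4% vs 12% in 54% of trials, 5% vs 15% in 67% and 6% vs 18% in 78%. It holds only for rarer events. The low power comes from a sample size chosen for vaccine response, and rewording does not change it.
- *No intervals will be reported for adverse events.* SAP 6.13.2 and 6.13.6 defer detail to compound level safety standards that are not among the documents and may specify intervals. Counts and percentages by arm are planned, so a reader could compute one.

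**Conclusion.** The label and the flagging sentence contradict each other, and Protocol 9.1 leaves no safety hypothesis for which the label could be reserved. With no drug effect, the 34 laboratory ANCOVAs alone produce at least one label with probability 82.5% under independence, about 71–80% with clustered analytes, and 70%, 54% or 45% at a common correlation of 0.3, 0.5 or 0.6. The vital signs would raise the independent figure to 86.5%, but their ANCOVA appears in SAP 6.1.2 and not in Table KGAK.6.10, so they are best kept out of the main count. Treatment-emergent laboratory tables and adverse event terms would add to it.

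The consequence is modest. No co-primary interval, stopping rule or trial decision depends on the label. It should be changed because it misdescribes the strength of safety findings and is easy to correct. The missing adverse event interval is a secondary point, limited to what SAP 6.1.2 and 6.13.2 name.

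**What to change.** In SAP 6.13, replace the label with: *will be flagged for medical review; flags are unadjusted and are not evidence of a treatment difference on their own*. Keep the two cautionary sentences.

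In SAP 6.13.2 and 6.13.6, add the risk difference with a 95% CI beside the Fisher p-value for the adverse event overview and the adverse events of special interest. The Newcombe method, already planned in stratified form for the co-primary endpoints, would serve. If the compound level standards already provide such an interval, a cross-reference is enough.

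The cost is slightly wider tables and a departure from compound-level stock wording. No new data are needed, and no test, threshold or analysis population changes. Because SAP Version 3 follows the Week 16 database lock, the revision history should record this as a change of wording and display only.

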6.13.1. Extent of Exposure

Exposure will be reported for participants in the Modified Safety Population and will be summarized by treatment group. Drug interruption time period due to the use of systemic rescue therapies will not be removed from study drug exposure calculations as described in compound level safety standards.

The duration of exposure will be calculated as

Duration of exposure (days)

$$\begin{aligned} &= \text{Date of last visit (scheduled or unscheduled) in the Treatment Period} \\ &- \text{Date of first dose} + 1 \end{aligned}$$

The number and percentage of participants in each of the following categories will be included in the summaries:

- $>0, \geq 7 \text{ days}, \geq 14 \text{ days}, \geq 30 \text{ days}, \geq 60 \text{ days}, \geq 90 \text{ days}, \geq 112 \text{ days}, \geq 120 \text{ days}$. Note that participants may be included in more than 1 category
- $>0 \text{ to } <7 \text{ days}, \geq 7 \text{ to } <14 \text{ days}, \geq 14 \text{ to } <30 \text{ days}, \geq 30 \text{ to } <60 \text{ days}, \geq 60 \text{ to } <90 \text{ days}, \geq 90 \text{ to } <120 \text{ days}, \geq 120 \text{ days}$

Additional exposure ranges may be considered if necessary. No p-values will be reported.

The summaries will also include the following information:

- Total exposure in patient years, calculated as

$$\frac{\text{Total exposure in patient years}}{\text{Sum of duration of exposures for all patients in treatment group}} = \frac{365.25}{365.25}$$

- Mean and median total dose. Total dose (in mg) is calculated by the number of active injections taken during the treatment period multiplied by dose. The total dose (in mg) taken during the Treatment Period will be calculated as follows: *Total lebrikizumab dose = Total number of active injections (including loading doses, if any) received in Treatment Period × 250 mg.*
- Total number of injections received will be derived based on the *Study Drug Administration* eCRF pages and dosing diary.

6.13.2. Adverse Events

A TEAE is defined as an event that first occurred or worsened in severity after baseline (date of first injection). The MedDRA Lowest Level Term (LLT) will be used in the treatment-emergent computation. The maximum severity for each LLT during the baseline period will be used as baseline. The treatment period will be included as postbaseline for the analysis. For events with a missing severity during the baseline period, it will be treated as “mild” in severity for determining treatment-emergence. Events with a missing severity during the postbaseline period will be treated as “severe” and treatment-emergence will be determined by comparing to baseline severity. For events occurring on the day of first taking study medication, it will be assumed to be posttreatment.

The planned summaries for AEs are provided in [Table KGAK.6.8](#) and are described more fully in compound level safety standards and in the AE-related PhUSE white paper (Analysis and Displays Associated with Adverse Events: Focus on Adverse Events in Phase 2-4 Clinical Trials and Integrated Summary Document [PhUSE 2017]).

Summary tables as described in [Table KGAK.6.8](#) will be presented for the following periods/analysis populations as indicated. Summary tables will include the number and percentage of participants reporting an event. For events that are gender-specific (as defined by MedDRA), the number of participants at risk will include only participants from the given gender.

Table KGAK.6.8. Summary Tables/Listing Related to Adverse Events

Analysis	Population (Section 6.1.1)
Overview of AEs	mS, S
Summary of TEAE by PTs	mS
Summary of TEAE by PTs occurring in $\geq 1\%$ of participants	mS
Summary of TEAE by PTs within SOC	mS
Summary of TEAE PTs by maximum severity	mS, S
Summary of SAE by PT within SOC	mS, S
Summary of AEs leading to treatment discontinuation by PT with SOC	mS
Summary of TEAE possibly related to study drug by PTs within SOC	mS

Analysis	Population (Section 6.1.1)
Listing of SAEs (including Death)	ITT
Listing of primary AEs leading to study treatment discontinuation	ITT
Listing of TEAE (for Japan submission only)	S
Listing of AE for Participants from Site 1883 and Site 1827	-

Abbreviations: AE = adverse event; ITT = Intent-to-Treat; mS = Modified Safety Population; PT = preferred term; SAE = serious adverse event; S = Safety Population; SOC = System Organ Class; TEAE = treatment-emergent adverse event.

Statistical comparisons will be performed using Fisher's exact test. Odds ratio will be provided. For AE related listings, AEs occurring on or after the date of Informed Consent and before the date of first injection in KGAK study will also be reported if proper.

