9.4.5. Safety Analyses

All AEs occurring during the study will be recorded and coded using the MedDRA dictionary. Treatment-emergent AEs (TEAEs) are defined as AEs with an onset date on or after the date of the first injection of study drug. TEAEs will be summarized by treatment group, including the number of participants reporting an event, system organ class, preferred term, severity, relationship to study drug, and seriousness for the safety population. All SAEs as well as AEs that led to study discontinuation will be listed by participant.

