6.1.2. General Considerations for Analyses

Treatment period starts after the first injection of study treatment at baseline visit (Day 1) and ends after participant completed Week 16 visit or the early termination visit (ETV) (between Day 1 and Week 16). Baseline will be defined as the last available value before the first injection for efficacy and health outcome analyses. In most cases, this will be the measure recorded at baseline visit (Day 1). If the participant does not take any injection, the last available value on or

prior to randomization date will be used. Change from baseline will be calculated as the visit value of interest minus the baseline value.

For Pruritus Numeric Rating Scale (NRS), Sleep-loss due to Pruritus, and Skin Pain NRS collected via eDiary, the baseline period is the 7-day window prior to the Baseline Visit (Day 1). A participant must have responses from at least 4 of 7 days to calculate a baseline weekly mean. If a participant has 3 or fewer responses, the baseline mean value will be considered missing. eDiary data for Pruritus NRS, Sleep-loss due to Pruritus, and Skin Pain NRS are mapped to study visit per [Appendix 1](#).

For the safety analyses, the following baselines will be used. For safety analyses using a baseline period, the baseline period is defined as the time from Screening Visit to the date/time of the first injection in Treatment Period.

- Treatment-emergent adverse events (TEAEs): baseline will be all results recorded during the baseline period
- Treatment-emergent abnormal laboratory and vital signs results: baseline will be all results recorded during the baseline period
- Change from baseline to last postbaseline observation or to each scheduled postbaseline visit for laboratory and vital signs results: baseline will be the last scheduled nonmissing assessment recorded during the baseline period

The randomization to treatment groups is stratified by baseline disease severity (IGA 3 versus 4) as described in Section [5.3](#). Unless otherwise specified, the statistical analysis models for Treatment Period will adjust for baseline disease severity.

For assessments of the secondary endpoints and other binary efficacy and health outcomes endpoints, the following will be provided

- Crude proportions for each treatment group along with the 95% two-sided asymptotic (that is, not continuity corrected) CIs

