6.13.5. Immunogenicity

An individual sample is potentially examined multiple times in a hierarchical procedure to produce a sample antidrug antibody (ADA) assay result and may yield a sample neutralizing ADA (NAb) assay result. Treatment-emergent ADAs (TE-ADAs) are defined as those with a titer 2-fold (1 dilution) greater than the minimum required dilution if no ADAs were detected at baseline (treatment-induced ADA) or those with a 4-fold (2 dilutions) increase in titer compared to baseline if ADAs were detected at baseline (treatment-boosted ADA). A participant is considered TE-ADA positive when at least 1 postbaseline ADA sample meets the definition of TE-ADA. A participant is evaluable for TE-ADA if there is at least 1 nonmissing test result for ADA for both the baseline and the postbaseline visits.

Compound level safety standards will be followed in the analyses of immunogenicity. Listings of immunogenicity assessments will be provided for the Safety Population. The summary of TE-ADA and NAb status will be produced for the Modified Safety Population, where the postbaseline period for reporting is the same as described for AEs in Section [6.13.2](#). Additional assessments of the relationship between immunogenicity and efficacy will be performed as part of the integrated analysis including other Phase 3 lebrikizumab AD trials.

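### The SAP closes the TEAE and TE-ADA windows at Week 16 or early termination, so non-serious AEs and first ADA positives from safety follow-up enter no by-arm summary that it names

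*SAP*

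**What the plan says.** **SAP.** The treatment period "ends after participant completed Week 16 visit or the early termination visit" (6.1.2). For TEAEs, 6.13.2 then states: "The treatment period will be included as postbaseline for the analysis". The TE-ADA and NAb summary in 6.13.5 follows suit, "where the postbaseline period for reporting is the same as described for AEs". The surrounding text agrees:

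- Section 6.13 bases safety evaluations on the treatment period for both safety populations.
- Section 6.13.2.2 summarizes SAEs and AEs leading to permanent treatment discontinuation over that period.
- Section 6.13.6 summarizes special safety topics over it unless otherwise specified.

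**Protocol.** Section 9.4.5 says that TEAEs "are defined as AEs with an onset date on or after the date of the first injection of study drug", with no end date. AEs are collected until participation ends (8.3.1). The Schedule of Activities (1.3) places AE and ADA collection at Visit 801, which is at Week 26 or about 12 weeks after the last injection. That visit is only for early terminators and participants not entering the extension. The TE-ADA definition (9.4.7) and the immunogenicity population (9.3) set no cut-off. The glossary in Appendix 10 differs from 9.4.5: it ties a TEAE to a defined treatment period.

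**The concern.** The trial collects safety data that its analysis plan gives no place in a comparison between arms. A completer's last dose is at Week 14, so the treatment-emergent window closes about two weeks later, while observation continues to Week 26 for anyone not rolling over. Under Protocol 7.1.2, participants who stop study drug permanently for reasons other than systemic rescue have an ET visit and then Visit 801. This group includes those who stopped for an AE or a hypersensitivity reaction, and their window closes at ET.

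Two things are at stake. A non-serious event starting after the last treatment-period visit, such as conjunctivitis or a herpes infection, is not counted by arm. It also falls outside the registry's category for other AEs, which requires the event to be treatment-emergent (SAP 6.18). Second, a participant whose ADA first turns positive at Visit 801 counts as TE-ADA negative in the summary, although SAP 6.13.5 makes one qualifying post-baseline sample enough for positive status.

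**Working it through.** **Inputs**

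- Last scheduled dose: Week 14 (Protocol 6.1.1).
- Window closes: Week 16 visit, or ET if earlier (SAP 6.1.2).
- Safety follow-up: Week 26, or about 12 weeks after the last injection (Protocol 1.3 and 4.1).
- Visit tolerance: ±3 days (Protocol 1.3).
- ADA sampling: six marks in the Schedule of Activities. The columns are displaced in the text available, and the best reading is Visits 2, 4, 8, 10, ET and 801.

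**The plan's own interval.** 26 − 14 = 12 weeks, which matches the stated 12.

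**Completer not entering the extension**

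- Window after last dose: 16 − 14 = 2 weeks.
- Follow-up outside the window: 26 − 16 = 10 weeks, or 70 days. With ±3 days at each end the range is 70 − 6 = 64 to 70 + 6 = 76 days.
- Share of post-first-dose observation: 10/26 = 38%.

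**Early terminator.** The documents do not fix the gap between last dose and ET, so assume 0 to 2 weeks. Visit 801 falls 12 weeks after the last dose, so 12 − 2 = 10 to 12 − 0 = 12 weeks lie outside the window. With a last dose at Week 4, Visit 801 falls at Week 16 and the share is 10/16 = 62.5% to 12/16 = 75%. With a last dose at Week 12, Visit 801 falls at Week 24 and the share is 10/24 = 42% to 12/24 = 50%.

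**Group level.** No rollover rate is given. If a share f of completers does not roll over, the fraction of completers' observation time outside the window is 10f/(16 + 10f). This is 0 at f = 0, 5/21 = 24% at f = 0.5, and 10/26 = 38% at f = 1. The values of f are assumptions that show the range; they are not estimates.

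**Where follow-up data can still appear.** These displays state no Week 16 cut-off:

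- SAEs: the ITT listing (SAP Table KGAK.6.8), and the registry table, which counts SAEs by treatment group whether or not they are treatment-emergent (6.18).
- AEs leading to study treatment discontinuation: the ITT listing (Table KGAK.6.8).
- ADA results: the Safety Population listing (6.13.5).
- Opportunistic, serious, herpes and parasitic infections: the Safety Population listing (Table KGAK.6.13).
- Conjunctivitis: the Safety Population listing (Table KGAK.6.14).
- ALT against bilirubin: the plot labelled for all periods (Table KGAK.6.11).

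The registry table is the only one of these that counts follow-up AEs by arm, and it does so only for serious events. None gives a by-arm count of non-serious follow-up AEs or of ADA first positive at Visit 801.

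**The case against.** The other side has real points.

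- **The protocol is not uniform.** The Appendix 10 glossary supports the SAP's window, and Protocol 9.4.1 lets the SAP change non-principal methods. A reader might infer that the SAP simply contradicts the protocol. The documents show instead two protocol definitions that disagree, with the SAP following one. Section 9.4.5 is nevertheless the operative analysis text. Section 9.4.1 asks for a justification of any change, and the SAP revision history gives none for this window; it records only a clarification of AE definition or scope in 6.13.2.
- **SAP 6.16 says other safety analyses will include all data collected by the final lock.** This sets the data cut and does not reopen the window in 6.13.2. It does leave the SAP unclear, which supports a clarification.
- **The compound-level safety standards may define a follow-up analysis.** They are not among the documents, so the finding is limited to what the SAP itself names.
- **A common window is defensible.** Visit 801 is attended only by early terminators and participants not rolling over. Pooling its samples into one TE-ADA rate would give a self-selected subset an extra, later sample. This stands, and it rules out the simple remedy of extending the window.
- **The data are not all lost.** A reader might infer that follow-up AEs of special interest and Visit 801 ADA results disappear altogether. The listings and the registry SAE table show otherwise.

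**Conclusion.** The gap is real and limited. Non-serious AEs that start in safety follow-up, and ADA first positive at Visit 801, enter no by-arm summary that the SAP names. The AE part rests on SAP 6.1.2, 6.13 and 6.13.2 against Protocol 9.4.5 and 8.3.1. The ADA part rests on SAP 6.13.5 against Protocol 9.3, 9.4.7 and the Visit 801 sample. The TEAE definition says nothing about ADA samples, so it cannot carry that part, although a reader might run the two together.

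The 38% describes completers who do not enter the extension. It is not a trial-wide figure, and early terminators have a different share that depends on when they stop. How far TE-ADA incidence is understated, if at all, cannot be computed. The co-primary vaccine endpoints at Week 16 are untouched and the study is descriptive, so this is a worthwhile and inexpensive improvement to safety reporting, not a threat to the main result.

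**What to change.** 1. Reconcile Protocol 9.4.5 and the Appendix 10 glossary with SAP 6.13.2 and 6.16. State one TEAE window with its end, and say whether the final-lock sentence in 6.16 changes it.
2. Keep the treatment-period tables as the main safety analysis.
3. Add separate follow-up-period summaries by arm for the Modified Safety Population: AEs by preferred term, SAEs, and AEs of special interest. Limit the denominator to participants who entered follow-up.
4. Report TE-ADA and NAb status including Visit 801 as its own labelled display beside the treatment-period rate.
5. Give the number entering follow-up in each arm, split into early terminators and completers not rolling over, so that the unknown share becomes visible.

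The cost is a few tables from data already collected. The downside is that they cover a self-selected subset, and the number in it may differ between arms. The titles and footnotes must say so, and arm differences in these tables should be read as descriptive.
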